## 14.0 BIOSTATISTICS

The primary objective of this study is to compare the rate of skeletal related events (SRE) from the date of randomization to death or 12 months, whichever occurs first, between patients who received standard of care versus upfront, early palliative RT to high-risk bone metastases. We expect 60-80% of the enrolled patients can be followed for 1 year. An SRE is defined as pathological fractures, spinal cord compression, or palliative radiotherapy and orthopedic surgery for bone pain. Data suggest that the event rate is around 60% in the standard of care arm . In our institutional experience, 75% of inpatient radiation consultation led to palliative radiation for painful bone

metastasis, an SRE. Furthermore, 61% of these lesions were diagnosed at least 4 months prior to undergoing RT. We believe 60% estimated event rate at 1-year is a conservative estimate.

The primary endpoint is a binary variable and the rate refers to proportion and is defined as the number of lesions that had SRE divided by the total number of target lesions. This analysis is lesion-based so an SRE (or no SRE) at one site does not affect the status of other sites from the same patient. We estimate that the investigational arm has the event rate around 30%. Radiation therapy is extremely effective in alleviating pain due to bone metastases with 70-80% pain control. By preventing the development of significant bone pain, which often leads to SREs, RT can effectively reduce SREs, To this end we will analyze at least 66 patients with valid SRE endpoint (randomized 1:1 to each arm) to achieve >80% power in detecting such a difference using a two-sample, one-sided proportion test with alpha<0.05. Since patients who withdraw before the endpoint can be evaluated will not be included in the analysis (i.e., it will NOT be an intent-to-treat analysis) we will over-accrue to account for withdrawals to ensure a minimum of 33 patients in each arm (subject to stratification, see Section 15.2) who can contribute the analyzable endpoint of SRE. We believe an additional 10% would be sufficient so totally we expect to randomize 74 patients. A small portion of patients (<15%) may have multiple lesions, in which case they will be treated as independent analysis units. In other words, the eventual effect sample size may be slightly higher than 66 because this objective will be analyzed per lesion.

Palliative radiation therapy is a well-established, frequently used treatment for patients with metastatic disease. It is often the standard of care for patients with symptomatic metastatic lesion. It is extremely unlikely to be more toxic or cause earlier deaths.

We expect to enroll all 74 patients within 2 years.

Secondary objectives will be analyzed per patient. Unless otherwise specified, all endpoints are defined within the time window from the date of randomization to death or 12 months, whichever occurs first.

To compare the number of hospitalizations related to SREs between standard of care and upfront, early palliative RT arms we will employ a Wilcoxon rank sum test.

To compare quality of life between standard of care and RT arms, using the Brief Pain Inventory (BPI) and EuroQol Group EQ-5D-5L forms, we will test the difference (between the two arms) of the survey results at the following time points: 3 months, 6 months, 12 months and optionally but recommended within one week of any SRE. The individual quantitative scores derived from the BPI, and the utility scores as well as the overall health scores derived from EQ-5D-5L, will be summarized at these assessment times using descriptive statistics (means and standard deviations, medians and quartiles). Differences between the two arms in terms of these quantitative scores at various time points of interest will be evaluated for both statistical and clinical significance using Wilcoxon rank

Page **22** of **30** Version: 2/26/16

sum tests and established minimally important differences (MIDs) for the various measures, respectively. For scale scores with no established MIDs, the "half standard deviation" rule will be applied (i.e., differences of a half standard deviation will be considered clinically significant). At the conclusion of the study data at each time point will be presented, the number of patients in each group at a given time point will be documented, and the mean EQ-5D-5L and BPI scores for each group will be plotted over time and longitudinal pattern will be examined with the possibility of proposing more complicated regression methods such as the linear mixed models. The categorical answers (e.g., YES vs NO) from EQ-5D-5L will be compared between the two arms using Fisher"s test at each time point as well and odds ratios together with confidence intervals will be computed. Other non-quantifiable answers (e.g., treatment receiving for pain) will be summarized descriptively. For the last question in BPI, the score for pain interference on the BPI Short Form is the mean of the 7 interference questions as long as at least 4 are completed.

For comparing pain-free survival and overall survival between the two arms, both of which are time to event endpoint (time from randomization to start of opioids or death which is not necessarily within 12 months from randomization), we will use log-rank test.

To evaluate CTCAE v4 toxicity events in the upfront RT arms, we will tabulate all toxicities and summarize the CTCAE v4.03 scores and present descriptive statistics. This will be done at 3 months, 6 months, and 12 months from randomization.

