## 10.0 EVALUATION DURING TREATMENT/INTERVENTION

All patients in Arm 2 (RT arm) will be assessed for toxicities according to CTCAE v 4.0 and pain score using BPI short form once every 5 treatment days. Only patients in Arm 2 (RT arm) will have radiation treatment related adverse event evaluation. Following randomization, all patients in Arm 1 and Arm 2 will be scheduled for follow-up at 3 months (+/- 4 weeks), 6 months (+/- 4 weeks), 12 months (+/- 4 weeks), and receive the following assessments:

- CBC with differential
- Imaging studies (Follow-up imaging at the discretion of the treating physicians)
- History and physical
- Performance status
- Adverse event evaluation (CTCAE V 4.0) (Excluding Arm 1 patients)
- BPI Short Form
- EQ-5D-5L

•

In the event of an SRE, the following assessments should be completed within one week. As it may not be feasible that the research team will be notified of all SREs within one week, or a patient may not be able to come to MSK, these assessments are optional, but highly recommended:

- CBC with differential
- Imaging studies (Follow-up imaging at the discretion of the treating physician)
- History and physical
- Performance status
- Adverse event evaluation (CTCAE v 4.0)
- BPI Short Form
- EQ-5D-5L

If patient is unable to come in for a follow-up appointment or within one week of an SRE occurring, a telephone follow-up will suffice. The CBC with differential, history and physical, performance status and imaging studies will be deferred. If the patient has had any of these assessments completed locally, records should be obtained to fulfill these requirements. If the attending physician is able, the adverse event evaluation can be completed over the phone.

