#### 13.0 CRITERIA FOR REMOVAL FROM STUDY

Patients will be removed from the study if any of the following criteria are met, after review by the principal investigator:

- 1. A change in the patient's medical status unrelated to RT results in the patient being unable to comply with the protocol.
- 2. Patient is unable to continue follow-up as outlined within the protocol
- 3. Patient is found to be ineligible based on the criteria in section 6.0 of this protocol.
- 4. Patient requests to withdraw from the protocol.
- 5. Patient death.

Otherwise, patients will continue on protocol until 12 months have elapsed since date of randomization or until an SRE occurs.

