# 16.1 Quality Assurance

An assigned (CRC) will work with the principal investigators to ensure proper adherence to the protocol, eligibility verification, informed consent and data accuracy.

Weekly registration reports will be generated to monitor patient accruals and completeness of registration data. Routine data quality reports will be generated to assess missing data and inconsistencies. Accrual rates and accuracy of evaluations and follow-up will be monitored periodically throughout the study period and potential problems will be brought to the attention of the study team for discussion and action.

Random-sample data quality and protocol compliance audits will be conducted by the study team, at a minimum of two times per year, more frequently if indicated.

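### The primary SRE comparison drops randomised patients who withdraw before the endpoint is evaluable, and no all-randomised or missing-outcome SRE analysis is planned, so withdrawal can bias it in a direction the documents do not determine

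*Combined protocol and SAP*

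**What the plan says.** Section 14.0 compares the proportion of target lesions with an SRE between arms, counting events "from the date of randomization to death or 12 months, whichever occurs first". The endpoint is binary and lesion-based, tested with a one-sided two-sample proportion test at 0.05. The design needs 66 analysable patients, 33 per arm.

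On withdrawal, the section states that "patients who withdraw before the endpoint can be evaluated will not be included in the analysis (i.e., it will NOT be an intent-to-treat analysis". Its remedy is to over-accrue: "We believe an additional 10% would be sufficient so totally we expect to randomize 74 patients".

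Section 13.0 lists reasons for removal from study. One is a change in the patient's "medical status unrelated to RT results in the patient being unable to comply with the protocol"; another reads "Patient is unable to continue follow-up as outlined within the protocol". The documents do not say whether such removals count as withdrawals for Section 14.0, or when an endpoint becomes evaluable.

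Section 12.2 brings patients enrolled on both arms into the pain-free and overall survival analyses. It says nothing equivalent for SRE. The rest of Section 14.0 covers secondary endpoints and toxicity only.

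**The concern.** Patients leave the primary comparison because of something that happens after randomisation, so the analysed groups need not be comparable even though the randomised groups were. Enrolling more patients replaces the lost numbers, but the replacements do not stand in for the people who left.

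The endpoint gives a specific route to bias. A lesion with an SRE has a known outcome from that day. A lesion without one has a known outcome only at 12 months or death. Patients who withdraw early therefore tend to be event-free when they leave, and removing them raises the analysed SRE proportion in their arm. If the arms lose different numbers, the two proportions rise by different amounts. Even with equal numbers lost, bias arises if the patients leaving one arm have a different underlying SRE risk from those leaving the other. A link between withdrawal and risk is plausible, because two of the Section 13.0 removal reasons concern declining medical status or inability to attend.

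What is at stake is the validity of the one-sided test in a small trial, where a few patients can move a result across 0.05. No planned analysis would show whether this had happened.

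**Working it through.** **1. The plan's own figures.** Inputs from Section 14.0: 60% vs 30%, one-sided alpha 0.05, power above 80%, 10% allowance. With pooled null variance and mean proportion 0.45:

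n per arm = [1.645·√(2·0.45·0.55) + 0.842·√(0.6·0.4 + 0.3·0.7)]² / 0.30² = (1.157 + 0.565)² / 0.09 = 32.9, so 33 per arm and 66 in total.

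Power at 33 per arm is 0.80. Inflation: 66/0.9 = 73.3, so 74. The design reproduces, and the allowance is 74 − 66 = 8 patients.

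**2. Type I error if all 8 exclusions occur.** Assumptions (not in the documents): 37 randomised per arm, one lesion per patient, constant and independent hazards for SRE (l), withdrawal (m) and death (d), with 12 months as one time unit, and a true 12-month SRE proportion of 45% in both arms. Deaths without SRE stay in the analysis as no SRE. The withdrawal hazard is set so that k patients of 37 are expected to be excluded:

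m/(l+m+d) · (1 − exp(−(l+m+d))) = k/37.

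Example without deaths at 6 control / 2 RT: l = −ln(0.55) = 0.598.
- Control: m = 0.239, SRE before withdrawal 0.405, excluded 6/37 = 0.162, analysed proportion 0.405/0.838 = 48.3%.
- RT: m = 0.074, SRE before withdrawal 0.435, excluded 2/37 = 0.054, analysed proportion 0.435/0.946 = 46.0%.

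The true proportion is 45% in both arms, so the apparent benefit of about 2.3 points is spurious.

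Simulated type I error of the planned one-sided pooled test (accurate to about ±0.002):

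| Excluded, control/RT | No deaths | 30% one-year mortality |
|---|---|---|
| 4/4 | 0.051 | 0.049 |
| 5/3 | 0.062 | 0.059 |
| 6/2 | 0.074 | 0.070 |
| 2/6 | 0.033 | 0.038 |

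**3. Equal numbers, unequal risk (illustration).** Exclude 4 of 37 per arm (w = 0.108). The analysed proportion is (0.45 − w·r)/(1 − w), where r is the SRE risk of those excluded.
- r = 40% in control and 50% in RT: 45.6% vs 44.4%, type I error about 0.062.
- r = 30% and 60%: 46.8% vs 43.2%, about 0.09. With these two swapped, about 0.027.
- r equal in both arms: no bias.

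These risks are assumed.

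**4. Bounds on a positive result.** Take 20/33 vs 10/33, a difference of 30.3 points, z = 2.47, one-sided p = 0.007. Add back 4 excluded patients per arm:
- all 4 control with SRE, no RT: 24/37 vs 10/37, difference 37.8 points, p = 0.0005;
- no control, all 4 RT with SRE: 20/37 vs 14/37, difference 16.2 points, p = 0.081;
- none of the 8 with SRE: 20/37 vs 10/37, p = 0.009.

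**The case against.** The exclusion is declared openly and budgeted for, so it is not a contradiction. It is also narrow. It covers only withdrawal before evaluability, and since the endpoint window closes at death, patients who die can be evaluated. Section 10.0 allows telephone follow-up and says "If the patient has had any of these assessments completed locally, records should be obtained to fulfill these requirements". Section 16.1 adds "Routine data quality reports will be generated to assess missing data and inconsistencies". These steps may reduce the loss, but they concern data collection, and neither says how a missing SRE outcome is analysed.

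The numerical effect depends on the assumed split. At 4/4 there is no inflation, at 5/3 it is about 0.01, and nothing in the documents points to 6/2. That stands, and it is why the size is called modest.

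Four stronger readings are tempting and are not supported:
- *That 8 exclusions are expected.* The 10% is described as sufficient. It is an allowance, not a forecast.
- *That the allowance is too small.* Section 14.0 says "We expect 60-80% of the enrolled patients can be followed for 1 year", but that figure does not separate deaths, which are evaluable, from withdrawals.
- *That the bias favours RT.* The documents do not say which arm would lose more patients, or of what risk.
- *That closer contact in Arm 2 will produce unequal withdrawal.* The extra assessments occur only during RT; the 3-, 6- and 12-month visits apply to both arms.

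It can also be argued that adding sensitivity analyses is enough. That would expose the problem but leave the headline test on a set selected after randomisation.

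**Conclusion.** The concern stands as a should-fix point. The omission is certain: the primary SRE analysis excludes randomised patients because of a later event, and no section supplies an all-randomised or missing-outcome SRE analysis. That bias is possible follows from the endpoint's structure. Its direction cannot be determined from the documents.

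Its size is uncertain and probably modest. If the full allowance is used, type I error runs from about 0.03 to 0.07 across the splits examined, assuming one lesion per patient, 45% SRE in both arms and withdrawal unrelated to risk. Unequal risk among those excluded can add to this, but by an amount the documents do not allow one to estimate. A reader might take p = 0.081 as the likely fate of a positive result; it is an extreme limit, requiring every excluded RT patient and no excluded control patient to have an SRE.

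**What to change.** In Section 14.0:
- Delete the statement that the analysis will not be intent-to-treat. Analyse all randomised patients by assigned arm, keeping the binary lesion-based endpoint.
- Count SREs that occur before withdrawal. Count death without SRE as evaluable without SRE.
- Pre-specify a rule for unknown SRE status after withdrawal, for example multiple imputation.
- Define when a withdrawn patient's endpoint counts as known, including through telephone contact or local records, and whether Section 13.0 removals are withdrawals.
- Add best-case/worst-case or delta-adjusted sensitivity analyses by arm, and report withdrawals with reasons by arm.
- Keep the evaluable-only proportion as a sensitivity analysis.

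A 12-month cumulative incidence with death as a competing event is an optional supportive analysis, not the default replacement. It changes the estimator, assumes non-informative withdrawal (so would not correct step 3), and its test was slightly anti-conservative in simulation with one lesion per patient: type I error 0.055 with 10% withdrawal per arm and 0.064 with none. Clustering was not simulated.

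Cost: rewording and modest programming, no extra patients. Power is 0.84 with 37 per arm if every outcome is obtained, against 0.80 with 33; power under imputation was not computed. The bounds may be wide, and patients who did not receive assigned RT may dilute the effect slightly.

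Separately, Section 13.0 ends participation at an SRE while Section 14.0 follows each lesion independently. Those passages should be reconciled.

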#### 15.2 Randomization

Patients will be randomized to the standard of care therapy arm or the early, upfront RT followed by standard of care therapy arm. For patients enrolled, immediately after consent is obtained, the CRC at MSKCC will register participants in the Clinical Trial Management System (CTMS). Once the participant's eligibility is established, the registration will be finalized and the participants will be randomized using the Clinical Research Database (CRDB). Randomization will be accomplished by the method of random permuted block, and will be stratified by disease histology and planned standard of care. After

Page **23** of **30** Version: 2/26/16

treatment arm is determined by randomization, the CRCs will notify physicians at MSKCC of the treatment arm within 24 hours of randomization. All data will be collected and analyzed at MSKCC.

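### The primary test counts several lesions of one randomised patient as independent observations, so its one-sided 5% level is not assured; the effect is small under the plan's own forecast and material with 3 to 5 lesions per affected patient

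*Combined protocol and SAP*

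**What the plan says.** Section 15.2 makes the patient the unit of randomisation: "Patients will be randomized to the standard of care therapy arm or the early, upfront RT followed by standard of care therapy arm". It uses permuted blocks, stratified by histology and planned standard of care.

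Section 14.0 makes the lesion the unit of the primary analysis. The endpoint is the share of target lesions that had an SRE, compared between arms "using a two-sample, one-sided proportion test with alpha<0.05". On patients with more than one lesion it says: "A small portion of patients (<15%) may have multiple lesions, in which case they will be treated as independent analysis units". It adds that "the eventual effect sample size may be slightly higher than 66 because this objective will be analyzed per lesion". It also says that "an SRE (or no SRE) at one site does not affect the status of other sites from the same patient". Section 4.1 allows up to 5 target lesions per patient, listed at randomisation and followed in both arms.

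Two other statements in section 14.0 might seem to deal with clustering, but neither reaches the primary test. One is "Secondary objectives will be analyzed per patient". The other, "with the possibility of proposing more complicated regression methods such as the linear mixed models", concerns only the BPI and EQ-5D-5L scores.

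**The concern.** Lesions in one patient share a tumour type, a systemic therapy, a survival time and a treatment arm. Positive correlation between their outcomes is plausible, although the documents give no value for it. The plain proportion test takes its standard error from the lesion count alone. If lesions of one patient tend to go the same way, that standard error can be too small and the p-value too low.

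The statement that one site does not affect the status of another is a scoring rule: each lesion gets its own yes or no. It does not make those outcomes statistically independent. At stake are the error rate of the trial's only primary test and the claim that extra lesions add to the sample size.

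**Working it through.** **1. The plan's own figure.** Inputs from section 14.0: event rates 60% and 30%, one-sided alpha 0.05, power above 80%. For the uncorrected z-test:

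n = [1.645·√(2·0.45·0.55) + 0.842·√(0.6·0.4 + 0.3·0.7)]² / 0.30² = (1.157 + 0.565)² / 0.09 = 32.9, so 33 per arm.

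Power at 33 per arm is 80.06% (normal approximation), and 66/0.9 = 73.3, so 74 randomised. The stated figures reproduce with one observation per patient. They borrow nothing from extra lesions.

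**2. Design effect without strata.** Assumptions, since the documents give neither: ICC 0.1-0.5, and exactly 15% of patients with k lesions (the others with one). Let k̄ be the mean lesion count and m = Σk²/Σk. Then

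- design effect: DE = 1 + (m − 1)·ICC
- effective sample size = 66·k̄ / DE
- approximate actual level = 1 − Φ(1.645/√DE)

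| 15% of patients have | k̄ | m | Lesions (66·k̄) | DE | Effective size | Level by formula |
|---|---|---|---|---|---|---|
| 2 lesions | 1.15 | 1.45/1.15 = 1.26 | 75.9 | 1.03-1.13 | 67-74 | 5.2-6.1% |
| 3 lesions | 1.30 | 2.20/1.30 = 1.69 | 85.8 | 1.07-1.35 | 64-80 | 5.6-7.8% |
| 5 lesions | 1.60 | 4.60/1.60 = 2.88 | 105.6 | 1.19-1.94 | 55-89 | 6.6-11.9% |

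Beta-binomial simulation of the pooled z-test (33 per arm, null rates 45% and 60%) gives 5.2-6.3%, 5.6-8.1% and 6.5-11.8%. At ICC 0 it gives about 5%. If 30% of patients have several lesions, the level is 5.4-7.1% with 2 each and 6.0-9.5% with 3.

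**3. Effect of the stratified randomisation.** Suppose the strata are balanced between arms and explain a share s of the between-patient variance. That part largely cancels in the comparison, but the unstratified test still counts it as noise. To a good approximation

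DE = 1 + ICC·[(m − 1) − s·k̄].

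The inflation disappears at s = (m − 1)/k̄. That is 0.26/1.15 = 23% with 2 lesions and 0.69/1.30 = 53% with 3. With 5 lesions it is 1.875/1.60 = 117%, which is impossible, so some inflation always remains. For example, with 2 lesions, ICC 0.5 and s = 0.5: DE = 1 + 0.5·(0.261 − 0.575) = 0.84 and the level is 3.7%. Simulation with s of 25-50% (assumed) gives about 3.7-5.2% with 2 lesions, 5.1-6.7% with 3 and 5.7-10.7% with 5.

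**4. Valid alternatives, 60% v 30%, 33 per arm, no stratum effect.** The clustered test is at lesion level, with a leverage-type corrected robust variance and a t reference; its level is about 4.6-5.2%. An uncorrected robust z-test has 5.5-6.6%. A t-test on each patient's share of lesions with an SRE has a level of 4.9-5.1% and power of 81.1-83.6% across all three settings.

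| 15% of patients have | Power, planned test | Power, clustered test |
|---|---|---|
| 2 lesions | 83.7-84.7% | 79.9-83.2% |
| 3 lesions | 85.1-87.9% | 77.8-85.6% |
| 5 lesions | 86.2-91.3% | 71.5-87.6% |

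Part of the planned test's power is bought with excess type I error.

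**5. Follow-up after the first SRE.** Everything above assumes that every lesion is followed throughout, in line with section 14.0, where "all endpoints are defined within the time window from the date of randomization to death or 12 months, whichever occurs first". Section 13.0, however, ends a patient's time on protocol at 12 months or when an SRE happens. If follow-up of the other lesions stopped at the first SRE, the planned test's level would be 3.7-4.7% with 2-3 lesions and 4.4-7.0% with 5 (15% of patients, ICC 0.1 and 0.5), so the error has no fixed direction.

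**The case against.** The strongest objection is the stratification. Histology and planned therapy are two of the main reasons to expect correlation, and section 15.2 balances both between arms. Step 3 shows that this can cancel the inflation with 2 lesions, or even leave the test conservative. That stands. It limits the claim, although perfect balance is optimistic in small strata, so the real offset would be partial.

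Second, the plan expects fewer than 15% of patients to have several lesions. With 2 lesions each and ICC 0.1, the excess is no larger than the discreteness of the test itself: its exact level with one lesion per patient is 5.16% at a null rate of 60% and 5.36% at 45%. That also stands. But the forecast has no source and is not an enrolment cap.

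Third, the version of the proportion test is not named, and an exact test could absorb mild clustering. Fisher's test has a level of about 3% at 33 per arm, but its power is 73.6%, so it is not the test that the plan was sized on.

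Three stronger readings are tempting and not supported:

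- A reader might infer that positive correlation necessarily pushes the level above 5%. Steps 3 and 5 show otherwise.
- A reader might infer that the trial is undersized because 66 relies on extra lesions. Step 1 shows that it does not.
- A reader might infer from the eligibility rule of more than 5 metastatic sites (section 6.1) that most patients have several target lesions. Those sites need not be bone or high risk, and the documents give no distribution of lesion counts.

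**Conclusion.** The independence rule is unsupported and the primary test is left unadjusted; confidence in that is high. Confidence in the direction and size of the resulting error is moderate, because the ICC, the lesion counts and the share of variance explained by the strata are all assumed.

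If the forecast holds and the affected patients have 2 lesions each, the level lies between slightly conservative and about one point too high, and the plan's remark on effective sample size is fair. With 3 lesions the excess is modest. With 5 it persists even after allowing for the strata, and the effective size can fall below 66. It also matters if the forecast is exceeded. The point should be fixed because the level of the primary test should not depend on a forecast of lesion counts.

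**What to change.** - Keep the lesion-level proportion and the 66/74 patients. Replace the independence rule with an analysis clustered by patient: GEE or a clustered two-sample proportion test, with a small-sample-corrected robust variance and a t reference.
- Adjust for the randomisation strata where their size allows. Without this, a clustered test would be conservative if the strata explain much of the variance.
- Prespecify the patient-weighted test as a sensitivity analysis. If it were made primary instead, the endpoint definition would need rewording, because it weights patients rather than lesions. The two can differ if lesion number is related to SRE risk.
- Reword the sample-size remark rather than only deleting it: the gain depends on lesion count and within-patient correlation (about 67-74 if 15% have 2 lesions, 55-89 if 15% have 5).
- State that the power above 80% (80.06%) is calculated with one unit per patient, and that the clustered test has about 80-83% power if 15% have 2 lesions and about 72-88% if 15% have 5.
- Reconcile section 13.0 with section 14.0 on whether a patient's other lesions are still followed after the first SRE.

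The cost is SAP wording and a few lines of code. Power falls by about 1.5-4 points against the planned test if 15% have 2 lesions and by about 4-15 points if 15% have 5, so it can drop below 80%.
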